4.8.2. Audits/Inspections

As part of quality assurance, the sponsor has the right to audit the trial sites and any other institutions involved in the trial. The aim of an audit is to verify the validity, accuracy and completeness of data, to establish the credibility of the clinical trial, and to check whether the trial subject's rights and trial subject safety are being maintained. The sponsor may assign these activities to persons otherwise not involved in the trial (auditors). These persons are allowed access to all trial documentation (especially the trial protocol, case report forms/trial database, trial subjects' medical records, drug accountability documentation, and trial-related correspondence).

The sponsor and all trial sites involved undertake to support auditors and inspections by the competent authorities at all times and to allow the persons charged with these duties access to the necessary original documentation.

All persons conducting audits and inspections undertake to keep all trial subject data and other trial data confidential.

4.9. Documentation

All data relevant to the trial are documented soon after measurement by the investigator in the trial database supplied. Entering data may be delegated to members of the local trial team. All changes made to the data are documented in an audit trail. The trial software has a user and role concept that can be adjusted on a trial-specific basis.

4.9.1. Data management

The IT infrastructure and data management staff will be supplied by Charité, department of Ophthalmology, CBF. The trial database will be developed and validated before data entry based on standard operating procedures. The data management system is based on commercial trial software and stores the data in a database. All changes made to the data are documented in an audit trail. The trial software has a user and role concept that can be adjusted on a trial-specific basis. The database is integrated into a general IT infrastructure and safety concept with a firewall and backup system. The data are backed up daily. After completion and cleaning of data, the database is locked and the data exported for statistical analysis.

The data will be entered online at the trial sites via the Internet. Plausibility checks are run during data entry, thereby detecting many discrepancies immediately. The Data Management will conduct further checks for completeness and plausibility and will clarify any questions with the trial sites electronically via the trial software. These electronic queries have to be answered by the trial site without unreasonable delay. Further details will be specified in the data management manual.

4.9.2. Archiving

All data in the database, informed consent forms and other important trial materials will be archived for at least 10 years in accordance with §13 (10) of the GCP-Verordnung.

5. Ethical and regulatory aspects

5.1. Independent ethics committee

The clinical trial will not be started before approval of the competent ethics committee concerning the suitability of the trial site and the qualifications of the investigators and trial team.

5.2. Ethical basis for the clinical trial

The present trial protocol and any amendments were and will be prepared in accordance with the Declaration of Helsinki of October 1996.

5.2.1. Legislation and guidelines used for preparation

The present clinical trial will be conducted in accordance with the published principles of the guidelines for Good Clinical Practice (ICH-GCP) and applicable legislation (especially the Federal Drug Law [AMG] and the GCP-Verordnung). These principles cover, amongst other aspects, ethics committee procedures, the obtaining of informed consent from trial subjects, adherence to the trial protocol, administrative documentation, documentation regarding the IMP, data collection, trial subjects' medical records (source documents), documentation and reporting of adverse events (AEs), preparation for inspections and audits, and the archiving of trial documentation. All investigators and other staff directly concerned with the study will be informed that domestic and foreign supervisory bodies, the competent federal authorities and authorised representatives of the sponsor have the right to review trial documentation and the trial subjects' medical records at any time.

5.3. Notification of the authorities, approval and registration

Before the start of the clinical trial, all necessary documentation will be submitted to the competent supreme federal authority for approval (Paul-Ehrlich-Institut [PEI]). The local authority will be informed about the trial according to German drug law.

Before the trial is started, it will be registered under www.clinicaltrials.gov a trial register approved by the World Health Organisation (WHO) (<http://www.who.int/ictpr/en/>).

5.4. Obtaining informed consent from trial subjects

Trial subjects may not be enrolled into the present trial unless they have consented to take part in the trial after having been informed verbally and in writing in comprehensible language of the nature, scope and possible consequences by a trial investigator or physician who is member of the trial team. Together with the consent to take part in the trial, the trial subject must also agree to representatives of the sponsor (e.g. monitors or auditors) or the competent supervisory or federal

authorities having access to the data recorded within the framework of the clinical trial. The trial subject will be informed of the potential benefit and possible side effects of the IMP. It must be clear to trial subjects that he or she can withdraw his or her consent at any time without giving reasons and without jeopardizing his / her further course of treatment.

The originally signed consent form and information sheet is archived in the investigator site file. Trial subjects receive copies of the written information sheet, confirmation of insurance with conditions, and the signed informed consent form. A copy of the written information sheet and the signed informed consent form will be filed in the patient's record.

The patient information sheet, informed consent form, all other documents handed out to the trial subject and any recruitment advertisements must be submitted for approval before use to the ethics committee. Part of the monitoring activities are to check that the most recent informed consent form was used before the trial subject was enrolled and that it was dated and signed by the trial subject himself or herself and signed and dated by the investigator or authorised physician.

5.5. Insurance of trial subjects

All trial subjects enrolled are insured in accordance with § 40 AMG under the group insurance contract of Charité University Medicine with HDI Gerling Versicherung (insurance company). The headquarters, policy number and telephone and fax number will be included in the patient information sheet.

5.6. Data protection

The provisions of data protection legislation will be observed. It is assured by the sponsor that all investigational materials and data will be pseudonymised in accordance with data protection legislation before scientific processing.

Trial subjects will be informed that their pseudonymised data will be passed on in accordance with provisions for documentation and notification pursuant to § 12 and § 13 of the GCP Regulations to the recipients described there. Subjects who do not agree that the information may be passed on in this way will not be enrolled into the trial.

6. Statistical methods and sample size calculation

6.1. Statistical and analytical plan

This is a two-arm, monocentre, therapeutic-exploratory clinical trial with 120 patients randomly assigned to treatment arms. Though the primary analysis is done at 5% significance level (two-sided). The essentials of the statistical analysis are outlined below. Further details will be laid down in the statistical analysis plan.

6.1.1. Trial populations

The first dataset for analysis is derived from the intention-to-treat (ITT) population. This dataset includes all trial subjects enrolled into the trial, randomised to treatment groups and received at least one injection of ranibizumab- no exclusions.

The second dataset for analysis is derived from the per-protocol (PP) population. This dataset includes all trial subjects who were treated according to protocol (i.e. they received at least 3 injections of ranibizumab and do not meet any exclusion criteria) and reached/provided at least one endpoint of main interest (i.e. after 6 months of follow-up).

The third dataset for analysis is the safety population. This population includes all trial subjects who received any ranibizumab treatment.

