4.6.1. Treatments to be given

In all patients (in both study arms) the diabetic macular edema will be treated with intravitreally given ranibizumab.

Dosage and administration of Ranibizumab

Injections are administered according to the current summary of product characteristics Lucentis®, i.e. monthly until maximum BCVA can be observed:

Starting at visit 1, ranibizumab will be administered intravitreally in a multiple-dose regimen of 0.5 mg of ranibizumab every month for a total of 3 injections and as a PRN treatment thereafter (subsequent injections until maximum BCVA is observed).

Injection is discontinued when

- no BCVA improvement in spite of treatment is seen after the first three injections (i.e. after three consecutive monthly visits)

BCVA assessments will take place monthly. Monthly injections are resumed when

- decrease in BCVA due to worsening of DME in the opinion of the investigator is observed

Injections are continued until BCVA improvement is seen after three consecutive monthly visits.

If a subject is unable to receive study drug because of medical or personal reasons, treatment should be resumed within 2 weeks of the scheduled treatment. If a subject is unable to receive study drug within 2 weeks of the scheduled treatment, the subject will be allowed to miss the scheduled dose and resume treatment at the next regularly scheduled time. Dosing should not occur more frequently than every 4 weeks. Missed doses will not be replaced.

Ranibizumab Injection

Procedures will be implemented to minimise the risk of potential adverse events associated with serial intraocular injections (e.g., endophthalmitis). Aseptic technique must be observed by clinic staff involved in the injection tray assembly, anesthetic preparation and administration, and study drug preparation and administration. In addition to the procedures outlined in the protocol, added safety measures in adherence to specific institutional policies associated with intraocular injections should be observed.

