4.6.7. Blinding, Unblinding

Observer-masking (assessment of BCVA, macular thickness, capillary drop-out) is done to guard against detection bias. Unblinding procedures are not applicable (treatment is not blinded).

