6.1.3. Primary target variable

The primary endpoint will be the change of best corrected visual acuity in ETDRS Letters score at month 12 when compared with baseline. This endpoint will be analysed by analysis of covariance (ANCOVA) with the baseline value as covariate (type II SS will be used since no interaction terms are included in the model).

The null hypothesis is:

$$H_0: \mu_{iDC} = \mu_{rDC}$$

and the alternative hypothesis is:

$$H_1: \mu_{iDC} \neq \mu_{rDC}$$

where μ_{iDC} is the mean of the differences in ETDRS Letters score between month 12 and baseline for the investigational arm (intensified diabetic control) and μ_{rDC} is the mean of the differences in ETDRS Letters score between month 12 and baseline for the control arm (regular diabetic control).

ITT population is used for the primary efficacy analysis. If no ETDRS Letter score is available at month 12 the closest measurement (could be before or after 12 month) which was at least after 3 months will be used for the analysis.

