6.1.4. Secondary efficacy variables

Different statistical methods will be applied for analysis of secondary endpoints.

For the number of treatments at 6, 12, 18 and 24 months, an ANOVA without any covariates will be applied at each endpoint 6, 12, 18 and 24 months.

The data of change in BCVA and macular thickness at 6, 12, 18 and 24 months are analysed by repeated measures analysis of variance (assuming missing at random, MAR). The missing values for BCVA and macular thickness are imputed by the last observation carried forward (LOCF). The treatment by time interaction will be included in both statistical models but the baseline value will only be included in the change in BCVA analysis since the macular thickness will not be adjusted by the baseline value in this analysis.

The change in BCVA and macular thickness with respect to baseline values is calculated at 6, 12, 18 and 24 months. For each time point, the change values are described statistically by mean, standard deviation, and 95% confidence interval.

Time to reach target HbA1c is evaluated by log-rank test and hazard ratio in terms of a Cox proportional hazard model. The results are visualised by Kaplan-Meier curves. No covariates are included in the model.

The number of neovascular complications in two treatment arms is compared by frequencies and a chi-square test if applicable (the chi-squared test will not be used when the absolute frequency in any of the cells of the contingency table is below 5), otherwise the Fishers exact test will be performed.

ITT population is used for all secondary efficacy analyses.

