6.1.6. Sensitivity and Subgroup analyses

A sensitivity analysis for the primary endpoint based on the PP population will be performed.

Another sensitivity analysis will assess the influence of the assumption of normality for the primary analysis by transforming the data with the natural logarithm. The ANCOVA described in section 6.1.3 will be applied in the same way on the transformed data.

The primary and secondary endpoint except number of neovascular complications and rates of ocular and of systemic AEs will be analysed by descriptive statistics and statistical methods mentioned above within the following subgroups defined by the following potentially prognostic baseline variables:

- HbA1c: $\geq 9\%$
- HbA1c: $\geq 7,5\%$, $< 9\%$

- HbA1c: $\geq 6,5\%$, $< 7,5\%$
- Intravitreal treatment with ranibizumab before trial entry (yes vs no)
- Size of macula edema $>400\mu\text{m}$
- BCVA (>65 vs ≤ 65)

For the sake of subgroup analysis, the ITT population will be used.

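### The set labelled ITT is a modified ITT set: it leaves out randomised patients who never receive ranibizumab, the background treatment of both arms, in an open-label trial

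*Combined protocol and SAP*

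**What the plan says.** Section 6.1.1 sets three conditions for the intention-to-treat set: enrolment, randomisation and a first injection ("randomised to treatment groups and received at least one injection of ranibizumab- no exclusions"). Section 6.1.3 states that "ITT population is used for the primary efficacy analysis", and section 6.1.4 that "ITT population is used for all secondary efficacy analyses". The subgroup analyses in 6.1.6 use the same set.

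The safety set in 6.1.1 applies the same criterion: "This population includes all trial subjects who received any ranibizumab treatment". For randomised patients the two sets therefore coincide.

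The only other population for the primary endpoint is narrower. Section 6.1.6 says "A sensitivity analysis for the primary endpoint based on the PP population will be performed", and the per-protocol set requires at least three injections. No analysis of all randomised patients is planned. Section 6.1 leaves further detail to a statistical analysis plan, but no text supplied changes the definition.

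Ranibizumab is common to both arms. Section 4.6.1 says: "In all patients (in both study arms) the diabetic macular edema will be treated with intravitreally given ranibizumab". The randomised contrast is intensified against regular diabetes control (sections 4.2 and 6.1.3). On blinding, section 4.6.7 reads "Unblinding procedures are not applicable (treatment is not blinded"; only the outcome assessors are masked. Table 2 in section 4.7.4.1 marks randomisation at screening, 1 to 7 days before the first injection at visit 1.

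**The concern.** A modified ITT set that requires one dose is usually defended on two grounds: the dose is of the randomised treatment, and the trial is blinded, so failing to start cannot depend on knowledge of the arm. Neither ground is available here. The condition concerns a co-treatment that both arms receive. A patient could take up the allocated diabetes programme, never be injected, and be removed from the comparison of the programmes.

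Patients are also not blinded. The control arm stays with its own physician, while the intensified arm takes on monthly diabetology visits in the first year (section 4.2). In Table 2 the arms already differ at visit 1: the intensified arm has blood glucose and blood pressure measured then, whereas the control arm's next such measurement after screening is at visit 3. Reasons for leaving before the first injection may therefore differ by arm. Concealed assignment protects the time before randomisation, and masked assessment guards against detection bias. Neither protects membership of the analysis set in the days between randomisation and injection.

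At stake is whether the comparison keeps the balance that randomisation created, and whether a reader can take the ITT label at face value.

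**Working it through.** **The plan's sample size.** Inputs from section 6.2: difference δ = 2.0 letters, SD σ = 3.5 letters, two-sided 5%, power 85%, allocation 1:1.

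- Normal approximation: n per arm = 2(1.960 + 1.036)² × (3.5/2.0)² = 55.0, so 55 per arm, 110 in total.
- Noncentral t: 56 per arm, 112 in total, power 85.02%. This matches the stated 112.
- Drop-out: 56 × 1.07 = 59.92, so 60 per arm. The allowance is 60 − 56 = 4 patients per arm for all losses.

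The planned size stands, and an all-randomised set leaves it at 120 (power 87.4% if all 120 are evaluable).

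**Possible shift from the exclusion.** The documents give no count of randomised but uninjected patients, so what follows is illustration. Assume that k of 60 patients are lost before injection in one arm only, and that their mean change lies D letters below the mean of their full arm. The mean of those retained then exceeds the full-arm mean by

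shift = k × D / (60 − k).

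The type I error comes from a two-sample t-test of size 60 − k against 60 with SD 3.5, taking the shift as the only difference. It is not the planned ANCOVA, so it gives the order of magnitude only.

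| k (assumed) | D, letters (assumed) | Shift, letters | Share of 2.0 | Two-sided type I error |
|---|---|---|---|---|
| 1 | 3.5 | 3.5/59 = 0.06 | 3% | 5.1% |
| 1 | 5 | 5/59 = 0.08 | 4% | 5.2% |
| 2 | 5 | 10/58 = 0.17 | 9% | 5.8% |
| 4 | 5 | 20/56 = 0.36 | 18% | 8.5% |
| 4 | 10 | 40/56 = 0.71 | 36% | 19% |

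The two lower rows spend an arm's whole 12-month drop-out allowance within a week. A D of 5 to 10 letters is 5/3.5 = 1.4 to 10/3.5 = 2.9 of the plan's SDs. Equal loss in both arms unrelated to outcome gives no shift, only fewer patients.

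**What the set definition alone changes.** For a missing month-12 score, section 6.1.3 accepts only a measurement taken after at least 3 months, and 6.1.8 rules out imputation that is not stated elsewhere. A randomised patient who leaves before injection and gives no later acuity measurement has no primary value under the present set or under an all-randomised one. Redefining the set changes the primary ANCOVA only for uninjected patients who are still measured after month 3. It also returns uninjected patients to endpoints such as the number of treatments and the time to target HbA1c.

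**The case against.** The case on the other side has real force.

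- **Patients stay in their arms.** A reader might infer that the analysis is not by randomised group. Nothing supports that: section 6.1.3 compares the arms as investigational and control ("where μ_{iDC} is the mean of the differences in ETDRS Letters score between month 12 and baseline for the investigational arm"), and no text moves a patient between them. The defect is incomplete inclusion.
- **The window is short and the incentive to leave is unclear.** It lasts days, both arms receive the same eye treatment, controls keep their usual diabetes care, and section 4.2 plans active follow-up against attrition. The documents do not say when a patient learns the allocation. Arm-dependent loss is possible, not shown.
- **The larger shifts stack assumptions.** They need one-sided loss, the full drop-out allowance and a large outcome difference. This is correct, and the lower rows of the table are not a forecast.
- **A new definition alone does little for the primary analysis.** This also stands, and it is why the remedy must include follow-up and a method for missing outcomes.
- **The no-exclusions phrase may mean no further exclusions among injected patients.** That reading is fair. The wording is then unclear rather than contradictory, but the injection condition remains. Likewise, the overlap with the safety set follows from that condition and is not a separate fault.
- **The question concerns patients treated with ranibizumab, in an exploratory trial.** This gives a first-injection condition some rationale as a secondary set. It does not justify the ITT label or the absence of an all-randomised analysis.

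**Conclusion.** The point holds as a matter of definition. The primary, secondary and subgroup analyses rest on a modified ITT set formed after randomisation by a co-treatment common to both arms, in an open trial. No all-randomised analysis stands beside it, and the one sensitivity population is narrower still.

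The size is a risk, not a finding. With 1 or 2 patients lost in one arm and a 5-letter difference, the shift is about 0.08 to 0.17 letters and the type I error stays below 6%. It becomes material only with around 4 one-sided losses whose outcomes differ clearly (about 0.36 to 0.71 letters against 2.0). Both the counts and the outcome differences are assumptions. A reader might infer that the primary result will be biased by a known amount; the documents do not support that. The change is worth making because it is cheap and makes the label true.

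**What to change.** 1. In section 6.1.1, define the ITT set as all randomised patients, analysed in their allocated arm regardless of ranibizumab received. Keep the condition of at least one injection for the safety set only.
2. State that the note in section 4.4 on follow-up after discontinued study treatment also covers patients never injected, so that acuity is collected up to month 12 where consent allows.
3. Report by arm the number of randomised patients never injected, and the number with no acuity value usable under the 6.1.3 rule.
4. Add a sensitivity analysis for those missing outcomes, for example multiple imputation or a likelihood-based model, with a range of assumed differences between patients with and without data.

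The first item is one sentence. The others cost a little more follow-up and analysis work, and a few patients with missing outcomes enter the primary set. The planned 120 patients do not change.

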6.1.2. Description of trial subject groups

Demographic variables and baseline values of study objectives will be summarised by treatment groups. Descriptive statistics in terms of mean, standard deviation and 95% confidence interval for continuous variables and frequency tables for discrete variables will be presented.

